#### Drug-induced liver injury

The liver function tests, namely AST, ALT, ALP, and total bilirubin, are used to assess possible drug-induced liver toxicity. The proportion of patients with PCSA values or ALT increase as defined in AESI section (see Section 2.1.4) during TEAE period by baseline status will be displayed by treatment group for each parameter.

An evaluation of drug-induced serious hepatotoxicity (eDISH) with the graph of distribution of peak values of ALT versus peak values of total bilirubin will also be presented using post-baseline values during TEAE period. Note that the ALT and total bilirubin values are presented on a logarithmic scale. The graph will be divided into 4 quadrants with a vertical line corresponding to 3 x ULN for ALT and a horizontal line corresponding to 2 x ULN for total bilirubin.

Listing of possible Hy's law cases identified (ie, patients with any elevated ALT>3 x ULN, and associated with an increase in bilirubin >2 x ULN, concomitantly or not) with ALT, AST, ALP, total bilirubin, and if available direct and indirect bilirubin will be provided.

The incidence of liver-related TEAEs will be summarized. The selection of PTs will be based on SMQ Hepatic disorder.

#### 2.4.5.4 Analyses of vital sign variables

The summary statistics (including number, mean, median, Q1, Q3, SD, minimum and maximum) of all vital signs variables in sitting position (raw values and changes from baseline will be calculated for each visit or study assessment (baseline, each post-baseline value of the treatment period, last on-treatment, worst on-treatment value and follow-up visit). In addition for some parameters of interest; mean changes from baseline with the corresponding SE could be plotted over time (at same time points excepted follow-up visit).

Vital signs without position filled in will only be used for the PCSA analysis described below.

The incidence of PCSAs at any time during the TEAE period will be summarized.

If any clinically significant signal is detected and needs further characterization, exploration of time to onset will be performed for selected PCSAs assessed during the TEAE period as described below to account for the differential exposure time in all patients.

The incidence rates of selected PCSA during TEAE period at 24, 52, 78, 104 and 156 weeks of exposure will be calculated with Kaplan-Meier methodology, using the midpoint of the time interval between the first assessment with PCSA and the previous assessment. Kaplan-Meier curves will be also provided. Only the first event (PCSA) will be counted. Patients without any event will be censored at the last assessment performed during the TEAE period.

# 2.4.5.5 Analyses of electrocardiogram variables

Not applicable

#### 2.4.6 Analyses of other endpoints

Binary endpoints defined in Section 2.1.5 will be described through patient counts and percentages in the safety population, overall and according to the treatment received during the parent study (placebo versus alirocumab (regardless of dose)). Kaplan-Meier curves will be provided for the "Time to" variables. Patients not meeting the event will be censored at the end of the treatment period. For the analysis of the time to the first of the two consecutive LDL-C events, patients without post-baseline LDL-C result or with only one post-baseline LDL-C result will not be included in the analysis.

# 2.4.7 Analyses of anti-alirocumab antibodies variables

The following summaries will be performed on the ADA population, overall as well as according to treatment received in the parent study (placebo versus alirocumab (regardless of dose)), taking into account all samples collected during the current study regardless of timing in relation to injections:

- ADA results (negative or positive) by time point;
- Neutralizing status (negative or positive) by time point for positive ADA;
- ADA titers using descriptive statistics (median, minimum and maximum) for positive ADA by time point;
- Number (%) of patients with treatment-emergent ADA positive response during the OLE period, overall and according to ADA status during the double-blind period (Pre-existing ADA, Negative ADA status and Treatment emergent ADA status)
- Number (%) of patients with persistent/transient/indeterminate treatment-emergent ADA positive response, overall and according to ADA status during the double-blind period (Pre-existing ADA, Negative ADA status and Treatment emergent ADA status)
- Time to onset of treatment-emergent ADA positive response during the OLE period using descriptive statistics.

Correlations between ADA parameters (eg, titers, treatment-emergent ADA positive status, neutralizing status) and safety and/or efficacy endpoints will be also explored (eg, scatter plot).

#### 2.4.8 Analyses of pharmacokinetic and pharmacodynamic variables

Not applicable

# 2.4.9 Analyses of quality of life/health economics variables

The analysis of data from EQ-5D instrument will be performed on quality-of-life population, overall as well as separately according to treatment received in the parent study (placebo versus alirocumab (regardless of dose)). Baseline is defined as the baseline of the parent study. Analysis window for efficacy parameters will be used to assign time points (see Section 2.5.4, Table 1).

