1.2 STUDY FLOW CHART

Day (D)/Week (W)/ Month (M)	W0 (End of DB treatment visit parent study) ^C (D1)	W 4	W 8	W 12	W 24	W 36	W 48	W 60	W 72 M18	W 84	W 96 M24	W 108	W 120 M30	W 132	W 144 M36	W 156	W 168 EOT 2Q 2017 M40	W176 EOS Call***
Visit Number	1	2	3	4	5	6*	7	8*	9	10*	11	12*	13	14*	15	16*	17	18
Visit Window (days)		±7	±7	±7	±7	±7	±7	±7	±7	±7	±7	±7	±7	±7	±7	±7	±7	±7
Design																		
Informed consent	Χa																	
Patient demography	Х																	
Inclusion/Exclusion Criteria	Χa																	
Physical examination	Х	Х		Х	Х		Х		Х		Х		Х		Х		Х	
Body weight	Х	Х		Χ	Х		Х		Х		Х		Χ		Х		Х	
IVRS/IWRS contact	Χa			Χ	Х	Х	Х	Х	Х	Х	Х	Χ	Х	Х	Х	Х	Χ	Х
Treatment																		
Injection at site	Χa																	
Review of diet	Х						Х				Х				Х		Х	
Investigational Medicinal Product (IMP) kit dispensation	Xa			Х	Х	Х	Х	Х	Х	Х	Х	Χ	Х	Х	Х	Х		
Compliance check of IMP (review patient diary ^e and treatment kit) and data collection on IMP administration	X (diary ^a)	X (diary only)	X (diary only)	Х	Х	Х	Х	Х	Х	Х	Х	Х	Х	Х	Х	Х	Х	
Concomitant medication	Х	Х	Х	Х	Х	Х	Х	Х	Х	Х	Х	Χ	Х	Х	Х	Х	Х	Х

Day (D)/Week (W)/ Month (M)	W0 (End of DB treatment visit parent study) ^C (D1)	W 4	W 8	W 12	W 24	W 36	W 48	W 60	W 72 M18	W 84	W 96 M24	W 108	W 120 M30	W 132	W 144 M36	W 156	W 168 EOT 2Q 2017 M40	W176 EOS Call***
Visit Number	1	2	3	4	5	6*	7	8*	9	10*	11	12*	13	14*	15	16*	17	18
Visit Window (days)		±7	±7	±7	±7	±7	±7	±7	±7	±7	±7	±7	±7	±7	±7	±7	±7	±7
Vital signs																		
Heart rate, blood pressure	Х	Х	Х	Χ	Х		Х		Х		Х		Х		Х		Х	
Safety																		
AE / SAE recording	Х	Χ	Χ	Χ	Х	Х	Х	Х	Χ	Χ	Χ	Χ	Χ	Χ	Χ	Χ	Х	Х
Central Laboratory Testing – Efficacy																		
Total-C, calculated LDL-C, HDL-C, TG, non-HDL-C	Х		Х		Х		Х		Х		Х		Х		Х		Х	
Apo B, Apo A-1, ratio Apo B / Apo A-1, and Lp (a)	Х						Х				Х		¥		Χ		Х	
Laboratory Testing – Safety																		
Central Hematology and chemistry	Х		Х		Х		Х		Х		Х		X		Х		Χ	
Central Creatine phosphokinase (CPK)	Х		Х		Х		Х		Х		Х		Х		Χ		Х	
Central Liver panel	Х	Х	Х	Χ	Х		Х		Х		Х		Χ		Χ		Х	
Local Urine pregnancy test	Xp	Х	Х	Χ	Х		Х		Х		Х		Χ		Χ		Х	

Day (D)/Week (W)/ Month (M)	W0 (End of DB treatment visit parent study) ^C (D1)	W 4	W 8	W 12	W 24	W 36	W 48	W 60	W 72 M18	W 84	W 96 M24	W 108	W 120 M30	W 132	W 144 M36	W 156	W 168 EOT 2Q 2017 M40	W176 EOS Call***
Visit Number	1	2	3	4	5	6*	7	8*	9	10*	11	12*	13	14*	15	16*	17	18
Visit Window (days)		±7	±7	±7	±7	±7	±7	±7	±7	±7	±7	±7	±7	±7	±7	±7	±7	±7
Laboratory Testing – Other																		

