9.3.1.3 Bioanalytical method

9.3.2 EQ-5D patient questionnaire

EQ-5DTM (13) is a standardized and generic instrument for measuring patient's health status and health-related quality of life (HRQoL) for clinical and economic assessments (See Appendix E).

EQ-5DTM instrument includes 5 items corresponding to the following domains: mobility, self-care, usual activities, pain/discomfort, and anxiety/depression.

Each item can take one of three responses: (1) "no problems", (2) "some problems", and (3) "severe problems".

Response to items can be converted to a standard utility score ranging between -0.594 representing "severe problems" and 1 representing "no problem".

EQ-5D endpoints include:

- Change in proportion of patients within each domain and response categories from baseline to Weeks 12, 24, 48, and End of OLETP.
- Change in mean EQ-5D utility scores from baseline to Weeks 12, 24, 48, and End of OLETP.

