11.3.3 Other analysis population

The anti-alirocumab antibody analysis will be performed on all treated patients (safety population) with a blood sample on Week 0 (baseline from parent study) and at least one evaluable blood sample for antibodies post IMP injection in the current study.

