11.4.4.1 Analyses of quality of life/health economics variables

The analysis of data from EQ-5D instrument will be performed on efficacy population.

Descriptive summaries for individual EQ-5D items.

• Frequency and proportion of patients within each EQ-5D domain and response categories will be summarized by visits on which EQ-5D is assessed (Weeks 0,12, 24, 48, and End of OLETP)

Descriptive summaries for EQ-5D utility scores.

• Response from individual items will be converted into a single EQ-5D utility score by means of a standard regression model. Summary statistics for the utility score (number, mean, median, Q1, Q3, standard deviation, minimum and maximum) will be calculated by visits on which EQ-5D is assessed (Weeks 0, 12, 24, 48, and End of OLETP). Change in mean EQ-5D utility scores from baseline (Week 0) to Weeks 12, 24, 48, and End of OLETP, will be calculated.

Further details will be provided in SAP.

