# 1.6 STATISTICAL MODIFICATIONS MADE IN THE STATISTICAL ANALYSIS PLAN

Not applicable.

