#### 2.3.3 Quality-of-life population

The analyses of quality of life will be performed on all enrolled and treated patients with a baseline (from parent study) and at least one matching post-baseline evaluation for any of the 5 dimensions.

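### The protocol measures EQ-5D change from Day 1 of the extension; the SAP measures it from the parent-study baseline, in a different population, and records neither change

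*SAP*

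**What the plan says.** **Protocol.** Section 9.3.2 defines the endpoint as "Change in mean EQ-5D utility scores from baseline to Weeks 12, 24, 48, and End of OLETP", without saying which baseline. Section 11.4.4.1 is more specific: "Change in mean EQ-5D utility scores from baseline (Week 0) to Weeks 12, 24, 48, and End of OLETP, will be calculated". The same section lists Week 0 with Weeks 12, 24, 48 and the end of the open-label period as the visits at which EQ-5D is assessed, and sets the population: "The analysis of data from EQ-5D instrument will be performed on efficacy population". In the flow chart (section 1.2) the first column is "W0 (End of DB treatment visit parent study", marked as Day 1 and Visit 1 of the extension, and an EQ-5D questionnaire is scheduled there.

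**SAP.** Section 2.1.9 defines change in utility score relative to the parent-study baseline, and section 2.4.9 repeats it: "Baseline is defined as the baseline of the parent study". Section 2.3.3 restricts the quality-of-life population to "all enrolled and treated patients with a baseline (from parent study" and at least one matching later evaluation. Section 2.4.9 assigns time points with Table 1 of section 2.5.4, whose first window is Week 4, starting on study day 15. Section 1.5 reports one change to the protocol's statistical section, the possible interim analysis. Section 1.6, on statistical modifications made in the SAP, reads "Not applicable".

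**The concern.** The two documents define different quantities under the same endpoint name. The protocol's quantity describes what happens to a patient's health status after entering the extension. The SAP's quantity runs from randomization in the parent study and so includes everything that happened there.

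This matters most for former placebo patients. Their change from parent baseline combines about 18 months without alirocumab with their first exposure to it. Presenting results by parent treatment, as SAP 2.4.9 plans, does not separate the two parts, because the parent period stays inside each patient's change. The planned cumulative distribution functions of change in utility have the same feature. Someone who reads the study report with the protocol in hand would expect the other quantity and would find no note explaining the difference.

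**Working it through.** No sample size, power or EQ-5D figure is stated for this endpoint, so there is no plan figure to reproduce. The check compares the texts and then splits the interval by time.

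**1. Which Week 0 does the protocol mean?** Section 11.4.4.1 puts Week 0 in a list of extension visits, and the flow chart places W0 at Day 1 of the extension with EQ-5D scheduled. Where the protocol wants the parent baseline for lipids it says so (sections 9.2.1 and 11.4.3); the EQ-5D text has no such qualifier. One passage points the other way: section 11.3.3 describes the antibody population as patients "with a blood sample on Week 0 (baseline from parent study". Usage is therefore not uniform, but for EQ-5D the context indicates Day 1 of the extension.

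**2. What the SAP's change contains.** For a patient with all three values, at extension week w:

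change (parent baseline to w) = change (parent baseline to Day 1) + change (Day 1 to w)

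The protocol's quantity is the last term alone.

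**3. Share of elapsed time.** Extension share = w / (P + w), where P is the time from parent baseline to Day 1.

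- P = 78 weeks for FH I, FH II and High FH. This is an assumption: the protocol says 18 months, and SAP 2.4.4.2 uses parent Week 78 as the end-of-parent value.
- P = 78 + 8 = 86 weeks for Long Term (LTS11717), which has an 8-week follow-up before Day 1 (protocol 6.1).
- Week 168 is the longest planned treatment; many patients may end earlier.

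| Extension week | P = 78 | P = 86 |
|---|---|---|
| 12 | 12/90 = 13.3% | 12/98 = 12.2% |
| 24 | 24/102 = 23.5% | 24/110 = 21.8% |
| 48 | 48/126 = 38.1% | 48/134 = 35.8% |
| 168 | 168/246 = 68.3% | 168/254 = 66.1% |

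The extension share passes one half once extension time exceeds 78 (or 86) weeks. These are shares of time, not of EQ-5D change.

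**4. Is a parent-baseline EQ-5D available?** Protocol 10.1.1.1 lists EQ-5D among procedures already planned at the parent end-of-treatment visit for FH I, FH II and High FH. For Long Term it appears only among the procedures added for the extension. Neither document states that EQ-5D was collected at baseline in any parent study. The protocol's parent-study table gives 486 + 249 + 107 + 385 = 1,227 randomized heFH patients, of whom Long Term supplied 385/1,227 = 31.4%.

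**5. What the SAP does elsewhere.** Section 2.1.1 already defines a baseline for the extension. Section 2.4.5 already reports laboratory and vital-sign changes from both baselines. EQ-5D gets only the parent one.

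**The case against.** The strongest defence has four parts.

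- **The protocol is loose about baselines.** Section 9.3.2 does not qualify the word, section 11.3.3 ties Week 0 to the parent study, every lipid endpoint uses the parent baseline, and section 11.4.4.1 leaves further details to the SAP. The SAP may be harmonising. This explains how the difference arose, but section 11.4.4.1 names Week 0 in a list of extension visits, and replacing a named baseline and population is more than a detail.
- **The parent baseline has a merit of its own.** It is the only value that precedes treatment for everyone. On Day 1, former alirocumab patients from three studies come directly from double-blind treatment, and those from Long Term come from an 8-week follow-up. This stands, and it is a reason to show both changes and not to rank one as the main analysis.
- **The SAP's change log need not be complete.** Section 1.5 speaks of a major change made by amendment, and the heading of section 1.6 can be read as covering changes to the SAP itself, in a first version. So the SAP cannot fairly be said to assert that nothing differs from the protocol. It remains true that neither section records these two differences.
- **The stakes are low.** EQ-5D is outside the primary and secondary objectives, is summarized descriptively, and carries no test. This also stands.

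Three stronger readings are tempting, and the documents do not support them. A reader might infer that the reported change mostly reflects the parent study; that rests on elapsed time alone, fails even on time at Week 168, and cannot be checked without EQ-5D values. A reader might infer that the Day 1 questionnaire goes unused; but Table 1 has no Week 0 row for any parameter, baseline values are defined separately, and under a parent baseline Day 1 could itself count as a later visit. The SAP simply does not say whether it is tabulated. A reader might infer that patients are lost for want of a parent value; that is possible, particularly for Long Term, but not shown.

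**Conclusion.** The conflict is real and minor. The protocol measures EQ-5D change from Day 1 of the extension in the efficacy population; the SAP measures it from the parent-study baseline in a population that requires a parent value; and neither difference is recorded. As planned, the change in utility mixes the parent period with the extension and does not isolate within-patient change during the extension, most notably for former placebo patients.

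In time, the parent period is the larger part of the interval at Weeks 12, 24 and 48 and the smaller part at Week 168. In EQ-5D units the size is unknown. The conclusion rests on reading Week 0 as Day 1 of the extension; the time shares also rest on taking 18 months as 78 weeks. No type I error, power, safety conclusion or lipid conclusion is affected.

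**What to change.** - Add to SAP 2.1.9 and 2.4.9 the change in EQ-5D utility from Day 1 of the extension to Weeks 12, 24, 48 and the end of the open-label period, as the protocol states. Include all treated patients with a Day 1 value and a later value, whether or not a parent value exists.
- Tabulate the Day 1 value as a time point, for the items and for the utility score.
- Keep change from parent baseline beside it, with a note that Day 1 is not a pre-treatment value for former alirocumab patients.
- Confirm for each parent study, and in particular Long Term, whether a baseline EQ-5D exists, and report how many patients have one.
- Record the change of baseline and the change of population in SAP 1.5 or 1.6. This includes the population proposed here, which is also not the protocol's efficacy population.

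The cost is one extra set of descriptive summaries from questionnaires that are already scheduled. No new visits or data are needed, and the approach matches what SAP 2.4.5 already does for laboratory and vital-sign data.

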#### *Individual EQ-5D items*

Response for each one of the 5 EQ-5D items will be summarized by visit using tables which will contain frequency and proportion of the population reporting level 1 (no problems), level 2 (some problems) and level 3 (extreme problems) and by item.

#### *EQ-5D utility score*

The raw value and the change from baseline of the utility score will be summarized using mean, median, Q1, Q3, SD, minimum and maximum for each post-baseline visit. Cumulative distribution functions for the change in utility score from baseline will be displayed over time.

#### 2.5 DATA HANDLING CONVENTIONS

# 2.5.1 General conventions

#### Medical history

"Peripheral Arterial Disease" history is defined as follows, using combinations of the corresponding pre-listed medical history items of the e-CRF page "Cardiovascular history and cardiovascular risk factors" of the parent study:

- Intermittent claudication (linked to PAD) TOGETHER WITH ankle-brachial index  $\leq 0.90$  Or
- Intermittent claudication (linked to PAD) TOGETHER WITH peripheral revascularization procedure (angioplasty, stenting) for PAD or peripheral revascularization surgery (arterial bypass) for PAD

Or

• Critical limb ischemia TOGETHER WITH peripheral revascularization procedure (angioplasty, stenting) for PAD or thrombolysis for PAD or peripheral revascularization surgery (arterial bypass) for PAD.

### Date of last dose of IMP

The date of the last injection is equal to the last date of administration reported on injection administration case report form page, or missing if the last administration date is unknown.

#### Renal function formulas

eGFR value will be derived using the Modification of the Diet in Renal Disease (MDRD) equation:

 $175 \times$  (creatinine in  $\mu$ mol/L / 88.4)-1.154 × (age in years)-0.203 (x 0.742 if female, x 1.212 if race is "black or african american").

# Lipids variables, laboratory safety variables, Hs-CRP

For data below the lower limit of quantification (LLOQ) / limit of linearity, half of the lower limit value (i.e., LLOQ/2) will be used for quantitative analyses. For data above the upper limit of quantification (ULOQ) / limit of linearity, the upper limit value (i.e., ULOQ) will be used for quantitative analyses.

#### 2.5.2 Data handling conventions for secondary efficacy variables

See Section 2.1.3.

# 2.5.3 Missing data

For categorical variables, patients with missing data are not included in calculations of percentages unless otherwise specified.

# Handling of baseline definition if time of first double-blind administration or time of assessment at Week 0 visit of parent study is missing

If the time of the first double-blind administration or the time of assessment at Week 0 visit of parent study is missing then the baseline value is defined as the last available value obtained before or on the day of the first double-blind IMP administration.

# Handling of baseline definition of the current study if time of first open-label administration or time of assessment at Week 0 visit of the current study is missing

If the time of the first open-label administration or the time of assessment at Week 0 visit of the current study is missing then the baseline value of the current study is defined as the last available value obtained before or on the day of the first open-label IMP administration.

# Handling of computation of treatment duration and compliance if investigational medicinal product first or end of treatment date is missing

If the last or first open-label injection date is missing, the exposure duration and compliance will be left as missing.

# Handling of safety and efficacy analysis periods and survival analysis if investigational medicinal product end of treatment date is missing

If the last injection date is missing, then this date is imputed to the earliest between

- the last day of the month and year, when applicable or else the 31st of December of the year,
- the date of the end of treatment visit,
- and the date of the last contact,

for the purpose of safety and efficacy analysis period start and/or end.

# Handling of medication missing/partial dates

No imputation of medication start/end dates or times will be performed. If a medication date or time is missing or partially missing and it cannot be determined whether it was taken prior or concomitantly, it will be considered a prior, concomitant, and post-treatment medication.

#### Handling of adverse events with missing or partial date/time of onset, worsening, seriousness

Missing or partial AE dates and times will be imputed so that if the partial AE date/time information does not indicate that the AE started prior to treatment or after the TEAE period, the AE will be classified as treatment-emergent. These data imputations are for categorization purpose only and will not be used in listings. No imputation is planned for date/time of AE resolution.

